## Methods

### *Patient*

The present study was approved by the Ethics Committee of the VGHKS (No.VGHKS19-CT9-11). All patients were recruited from the VGHKS between October 2019 to January 2022. All patient provided informed consent before being enrolled in the study.

Inclusion criteria was: [1] Aged>20 [2] Scheduled to received operation that required general anesthesia with endotracheal tube [3] ASA I, II. Patient with fallow condition would be excluded: [1] Emergent surgery [2] pregnant [3] Limited mouth opening [4] Poor dental condition [5] Airway obstruction (oral tumor, hypopharyngeal cancer....etc) [6] Deep neck infection [7] Allergic to any anesthetic agent.

### *Anesthesia protocol*

After the patient entered the operating room, monitor would be setup with electrocardiogram, non-invasive blood pressure, oxygen saturation, end-tidal carbon dioxide (PEtCO2). Intravenous access would then be established. Induction would be started right after setting the patient to sniff position and well pre-oxygenated. Endotracheal tube selection would fallow rules as below: Inner diameter 7.0mm for female patient, 7.5mm for male patient. As nasal endo, Inner diameter 6.5mm for female patient, 7.0mm for male patient. As Double lumen endotracheal tube 35 Fr for female patient, 37 Fr for male patient. Adjusted by patient's height as physician's clinical experience. Fentanyl 1-2 ug/kg, propofol 1.5-2mg/kg, rocuronium 0.6-1mg/kg or cisatracurium 1-2 mg/kg were administered intravenously as induction agent. Intubation was performed 3 minutes after muscle relaxant injection. Mechanical ventilation started right after the airway establishment.

During intubation, physician placed the tip of the video conventional Macintosh

blade at base of epiglottis to achieve glottic opening. Cormack-Lehane grade was then record as conventional attempt. Then physician placed the tip of the blade under the epiglottis and lift it to achieve glottic opening. Cormack-Lehane grade was record as Miller's attempt. Also, increased lifting force, BURP maneuver would be record if applied. If both attempts failed to intubate the patient, the process would switch to emergent difficult airway protocol and the patient would drop out the research. Three physicians attended this research had experience of anesthesia for 4, 6, 15 years with success intubation experience > 300+ cases.

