### *Statistics*

The patient data were presented as frequency and percentage for categorical variables or mean and standard deviation for continuous variables. The Cormack-Lehane grading during Miller versus Macintosh approaches was compared using the McNemar-Bowker test. The test was 2-tailed and  $P < 0.05$  was considered statistically significant. Data analyses were conducted using SPSS 26 (IBM SPSS Inc, Chicago, Illinois).

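### Every patient is graded in the Macintosh position first and the Miller position second, so the planned paired test cannot separate technique from look order; restate the comparison and declare the fixed order as a limitation.

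*Combined protocol and SAP*

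**What the plan says.** The Anesthesia protocol section describes a single procedure. The blade tip is placed at the base of the epiglottis, the view is graded, and the second view follows: "Cormack-Lehane grade was then record as conventional attempt. Then physician placed the tip of the blade under the epiglottis and lift it". After that, "Cormack-Lehane grade was record as Miller's attempt". No other order is described, and nothing mentions randomised, alternated or counterbalanced views.

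On manoeuvres that can change the view, the same section says "Also, increased lifting force, BURP maneuver would be record if applied". It does not say at which look they were used or recorded.

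The Statistics section names one between-technique analysis: "The Cormack-Lehane grading during Miller versus Macintosh approaches was compared using the McNemar-Bowker test". It is two-tailed at 0.05, with no term or stratum for order and no mention of order as a limitation.

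The Patient section reports enrolment in the past tense: "All patients were recruited from the VGHKS between October 2019 to January 2022".

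**The concern.** Pairing removes differences between patients. It does not remove differences between a first and a second look at the same patient. The second look could be better because the operator has already seen the airway, has adjusted the lift or has had more time for relaxation to develop. It could be worse because the tissues have already been manipulated. If lifting force or BURP was used more at one look than at the other, the looks also differ in something besides blade position.

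The planned test credits all of this to technique. It can therefore report a technique difference where there is none, or hide a real one. As this is the plan's only comparison of the two techniques, the trial's main claim depends on an unstated assumption that look order has no effect.

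**Working it through.** **Inputs from the document.** The sequence of views (Anesthesia protocol); the test, its sidedness and its level (Statistics). The document gives no sample size, power, effect size or grade distribution, so there is no figure of its own to reproduce.

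**Step 1: what the contrast estimates.** On an underlying scale, write the view of patient *i* at a given look as

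Y = a_i + τT + πP + error,

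with T = 1 for the Miller position and P = 1 for the second look. Here look 1 always has (T, P) = (0, 0) and look 2 always has (1, 1). The within-patient difference is therefore τ + π + error.

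**Step 2: rank.** With columns (intercept, T, P):

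- Fixed order: the distinct rows are (1,0,0) and (1,1,1). Rank 2 for 3 parameters, so τ cannot be estimated apart from π.
- Random order: rows (1,1,0) and (1,0,1) are added. Rank 3, so τ and π separate.

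This result needs no assumed number. A larger sample or a different paired test does not change it.

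**Step 3: what the test responds to.** The Bowker statistic is the sum over i < j of (n_ij − n_ji)² / (n_ij + n_ji), with 4 × 3 / 2 = 6 df for four grades. Its null is symmetry, p_ij = p_ji. A non-zero π breaks symmetry even when τ = 0.

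**Step 4: illustration under assumed inputs.** Assumed: grades I–IV at 60/28/10/2%, latent correlation 0.7 between looks, no technique effect, fixed order. The document does not say how pairs of cells that are both empty enter the df, so both conventions are shown. Entries are the percentage of simulated trials with P < 0.05, for N = 100/200/300 (40,000 trials per setting).

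| Second-look shift (latent SD) | 6 df | Empty pairs dropped |
|---|---|---|
| 0 | 0.6 / 1.5 / 2.1 | 2.5 / 3.2 / 3.6 |
| 0.05 | 0.8 / 2.3 / 3.8 | 3.2 / 4.6 / 6.1 |
| 0.10 | 1.6 / 5.9 / 10.8 | 5.6 / 10.3 / 15.4 |
| 0.25 | 13.9 / 49.8 / 77.1 | 28.4 / 61.6 / 83.2 |

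No safe shift can be read from this table. A 0.05 SD shift reaches 7.2% (6 df) or 9.4% (dropped) at N = 600, and 12.3% or 14.3% at N = 1000. The correlation matters too: at N = 200 and 0.25 SD, correlations of 0.5/0.7/0.9 give 36.9/49.8/83.1% (6 df).

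**Step 5: random order for contrast.** With 1:1 random order and a common shift, the highest rate was 2.8% (6 df) or 3.4% (dropped). Repeat runs reached 3.1% and 3.5%, which is within simulation noise.

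**Step 6: masking.** Suppose Miller is truly better by 0.25 SD. With no order effect, the fixed-order test detects this in 14/50/77% of trials (6 df, N = 100/200/300). If the second look is 0.10 SD worse, the net shift is 0.25 − 0.10 = 0.15 SD and detection falls to 4/14/27%. With empty pairs dropped the figures are 28/62/83% and 10/22/35%.

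**Step 7: a check with different assumptions.** First-look grades 50/30/15/5%; at the second look 20% improve by one grade unless already grade I, and 5% worsen by one unless already grade IV; no technique effect. Fixed order rejects in 6/14/34% of trials at N = 50/100/200, against 2/3/3% when the order is counterbalanced.

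**The case against.** The best case against this point is that no order effect has been shown. The same blade is repositioned in the same patient under the same induction, and the document gives no evidence that a second look differs, in either direction. What is established is that the technique effect cannot be isolated, not that the result is wrong. The rates in the tables rest on invented inputs, and some are below 5% (0.10 SD at N = 100 with 6 df gives 1.6%). All of that stands, and the simulations are no estimate for this trial. It does not answer the structural point: the plan gives no reason to assume the order effect is zero, and its only comparative test needs that assumption.

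It can also be said that calling this true of every patient goes too far, because the text does not settle whether a Miller grade is taken when the first attempt already intubates. The procedure as written is unconditional, so both grades for all patients is its literal reading. If some patients have only a first grade, the pairs are a selected subset and the illustration does not describe them. The aliasing still holds in every pair that exists.

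Finally, with recruitment over, no remedy recovers the separation, and a subset without manoeuvres may itself be selected. Both are true. They limit what can be repaired, not what should be claimed.

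**Conclusion.** The concern holds. As written, technique and look order are completely aliased (rank 2 for 3 parameters), and a significant McNemar-Bowker result supports only the statement that the second grade differs from the first. This conclusion rests on the single sequence described and on the absence of any counterbalancing or order term; nothing in the document contradicts either.

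The size and direction of any bias are unknown. The simulated rates depend on assumed grades, correlation, shift and sample size, and show only that a modest second-look effect could produce or hide a significant result. The point should be fixed before the comparison is reported, because it changes what the trial can conclude.

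**What to change.** For the patients already enrolled:

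1. In the Statistics section, restate the comparison as the change in Cormack-Lehane grade on a second look with the epiglottis lifted, after a conventional look. Do not attribute the change to technique alone, and state the fixed order as a limitation.
2. Report the 4x4 table of first against second grade, with the direction of change and the number of patients who have both grades.
3. If lifting force and BURP were recorded separately for each look, also show, descriptively, the pairs in which neither was applied. This examines one way the looks may differ; it does not remove order confounding.
4. As a separate minor point, state whether the Miller grade was recorded when the first attempt achieved intubation.

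The cost is a few sentences, one table and one descriptive subset, which will be smaller than the full set and not a random sample of it. The claim of a pure technique effect is given up.

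Only if patients remain to be enrolled, or in a follow-on study: randomise the order of the two views 1:1, blocked by operator, and analyse with a period term or stratify the paired test by order. This needs an allocation list. It does not cure unequal carry-over: under the same assumptions, a 0.25 SD shift in the Macintosh-then-Miller order only still gives rejection rates of 2.3/8.6/15.8% (6 df) or 6.7/14.2/21.8% (empty pairs dropped) at N = 100/200/300.

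### Does leaving the timing of added lifting force and BURP unstated undermine the paired comparison of Cormack-Lehane grades?

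*Combined protocol and SAP*

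**What the plan says.** Under Anesthesia protocol, the physician places the blade in the conventional position and a grade is taken: "Cormack-Lehane grade was then record as conventional attempt". The blade is then moved in the same patient: "Then physician placed the tip of the blade under the epiglottis and lift it to achieve glottic opening". A second grade follows: "Cormack-Lehane grade was record as Miller's attempt". Only after both gradings does the section turn to the manoeuvres: "Also, increased lifting force, BURP maneuver would be record if applied". It gives no timing relative to the grade, no blade position and no definition of increased force.

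Under Statistics, the analysis is a single two-sided test at 0.05: "The Cormack-Lehane grading during Miller versus Macintosh approaches was compared using the McNemar-Bowker test". The manoeuvres are not named there. The general sentence "The patient data were presented as frequency and percentage for categorical variables or mean and standard deviation for continuous variables" would cover a count of them.

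Under Patient, recruitment is described in the past tense: "All patients were recruited from the VGHKS between October 2019 to January 2022".

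**The concern.** Added lifting force and BURP act directly on the laryngeal view, and the view is the only outcome that is tested. The operator knows the blade position, and the order is always conventional first and Miller second, so equal use at the two positions cannot be taken for granted.

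Suppose grades were called after any help. More help at the Macintosh position would then shrink or hide a Miller benefit, and more help at the Miller position would create or inflate one. Equal help would create no false difference, but it would turn the question into a comparison of aided views. A reader of the plan alone cannot say with certainty which comparison the P value stands for.

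**Working it through.** The plan gives no sample size, power, effect size, grade distribution or frequency of manoeuvres, so it has no figure to reproduce. Three inputs come from the documents: one grade per position in the same patient, the McNemar-Bowker test, and a two-sided 0.05 level. Every other input below is an assumption.

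**1. Order of the text.** The sequence is: place the blade, record a grade; move the blade, record a grade; also record manoeuvres if used. Each grade follows directly from blade placement, and the manoeuvres are a further item after both. This does not exclude aided grading, but unaided grading is the more natural reading. Under it, manoeuvre use cannot affect either grade.

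**2. Shift in the difference if grades were taken after help.** Let p be the proportion of poor views (grades III-IV), u the share of poor views given help, and c the share of those corrected. Then

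difference = pMac(1 − uMac·c) − pMil(1 − uMil·c).

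With poor views of 15% against 7%, the true difference is 8.0 points.

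| Help used | u = 0.6, c = 0.6 (36% corrected) | u = 0.3, c = 0.3 (9% corrected) |
|---|---|---|
| Both positions | 0.0960 − 0.0448 = 5.1 points | 0.1365 − 0.0637 = 7.3 points |
| Macintosh only | 0.0960 − 0.0700 = 2.6 points | 0.1365 − 0.0700 = 6.65 points |
| Miller only | 0.1500 − 0.0448 = 10.5 points | 0.1500 − 0.0637 = 8.6 points |

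With 12% poor views at both positions (no true difference) and c = 0.6, the spurious difference is 0.12 × 0.6 × (uMac − uMil):

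- 60% against 60%: 0
- 60% against 40%: 0.072 × 0.2 = 1.4 points
- 60% against 20%: 0.072 × 0.4 = 2.9 points
- 60% against none: 0.072 × 0.6 = 4.3 points
- low case, 30% against none with c = 0.3: 0.12 × 0.09 = 1.1 points

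**3. False-positive rate of the McNemar-Bowker test, no true difference.** Assumptions: grades I-IV in 55/33/10/2% at both positions, latent correlation 0.7, c = 0.6, a corrected poor view becomes grade II, 3000 simulated trials per cell.

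| Patients | No help | 60/60 | 60/40 | 60/20 | 60/0 |
|---|---|---|---|---|---|
| 100 | 0.021 | 0.023 | 0.029 | 0.048 | 0.084 |
| 200 | 0.034 | 0.027 | 0.043 | 0.086 | 0.191 |
| 400 | 0.039 | 0.039 | 0.061 | 0.184 | 0.437 |

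With correlation 0.5 and 400 patients, the four helped columns are 0.030, 0.059, 0.152 and 0.347.

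A second model assumed grades in 50/30/15/5%, a one-grade scoring error in 20% of views, and help that improves a stated share of views of grade II or worse by one grade (3000 trials per cell):

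| Share improved, Macintosh vs Miller | 50 patients | 100 patients | 200 patients |
|---|---|---|---|
| 0% vs 0% | 0.021 | 0.025 | 0.030 |
| 20% vs 20% | 0.022 | 0.026 | 0.031 |
| 10% vs 20% | 0.030 | 0.054 | 0.097 |
| 10% vs 30% | 0.069 | 0.141 | 0.359 |
| 0% vs 30% | 0.154 | 0.401 | 0.798 |

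The models agree on the mechanism: equal use is harmless, and the error grows with imbalance and sample size. They differ widely on its size, because the size comes from the assumed inputs.

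**4. What a change could still achieve.** With recruitment dated October 2019 to January 2022, a new data field or a pause to call an unaided grade cannot be added for these patients. Ranking aided grades just below unaided ones would give eight categories and 8 × 7 / 2 = 28 off-diagonal pairs, against 4 × 3 / 2 = 6 now. The Bowker table would be sparse, so a paired sign test would be needed. That is possible only if help was logged by position.

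**The case for a change.** The strongest case for a change is that the order of sentences is not a definition. The manoeuvre sentence comes after both gradings, so it fits help given at either position, before or after the grade was called. Each position is used to open the glottis and the grade is then noted, which does not rule out an assisted view. An unblinded operator working in a fixed order makes unequal help plausible. With strongly one-sided help, the assumed models give false-positive rates of 0.44 at 400 patients and 0.80 at 200. One written sentence would settle the matter at almost no cost.

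The ambiguity stands, and so does the mechanism. The step to a required change does not. Serious distortion needs several things together: grading after help, clearly unequal use, frequent correction and enough patients. The documents show none of these. Naming the unaided view as primary would also choose one estimand over another, since a comparison of aided views is a legitimate question too. Nor would it settle the definition, because increased force has no stated threshold and the Miller position itself involves lifting.

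**Conclusion.** This is a gap in wording that analysts can fill sensibly, and no change to the plan follows. On the more natural reading, each grade is the view obtained by blade placement alone and the McNemar-Bowker comparison is unaffected. If grades were in fact aided, neither the size nor the direction of any bias can be derived from the documents. Under the assumed inputs of the first model, the false-positive rate stays near or below 0.05 with equal or mildly unequal use (at most 0.061, for 60% against 40% at 400 patients). It becomes serious only with clear imbalance in a larger sample. The second model is less forgiving, at 0.097 for 10% against 20% improved with 200 patients, but its inputs are equally unsupported.

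The plan already has manoeuvre use recorded and has a general rule for presenting categorical data, so a count can be reported without amendment. Whether the grades were aided, and whether help was logged by position, are facts for the trial report to state, as a limitation if need be. This conclusion rests on the sentence order reflecting practice. It would need another look if the investigators said that grades were called after help and that help was clearly commoner at one position.

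### Could Miller grades exist only for patients whose conventional attempt failed, tilting the paired test towards improvement?

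*Combined protocol and SAP*

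**What the plan says.** The Anesthesia protocol section sets out one sequence. The blade is placed in the conventional position and "Cormack-Lehane grade was then record as conventional attempt". The next step is "Then physician placed the tip of the blade under the epiglottis and lift it to achieve glottic opening", after which "Cormack-Lehane grade was record as Miller's attempt". No condition is attached to the second placement.

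The same section then gives a rule for leaving the study, which begins "If both attempts failed to intubate the patient". An earlier paragraph of that section notes that "Mechanical ventilation started right after the airway establishment".

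The Statistics section states one comparison: "The Cormack-Lehane grading during Miller versus Macintosh approaches was compared using the McNemar-Bowker test". It is two-sided at 0.05. The section does not define an analysis set and does not say what happens to a patient with only one grade.

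**The concern.** The test of symmetry needs two grades per patient. The drop-out rule uses the word attempt for something that can fail to intubate, so it can presumably also succeed. If the tube went in at the first successful attempt, the second view would be taken only when the conventional one had failed.

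The pairs would then be selected on a bad first grade. Patients with a good first grade and a worse second one would be almost absent, while those with a bad first grade and a better second one would all be kept. By regression to the mean, ordinary variation between two gradings would then appear as an advantage for the Miller approach. This would affect the only comparison the plan specifies, always in the same direction. The documents do not say in so many words that both grades come before the tube.

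**Working it through.** The plan gives no sample size, effect size, grade distribution or failure rate, so it has no figure of its own to reproduce. The check has two parts: what the sentences require, and how much would depend on the answer.

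**Reading the sentences together**

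| Sentence | Both views graded, then tube passed | Second view only after a first failure |
|---|---|---|
| "Cormack-Lehane grade was then record as conventional attempt" | Fits | Fits |
| "Then physician placed the tip of the blade under the epiglottis and lift it" | Fits as written | Needs an added condition |
| "Cormack-Lehane grade was record as Miller's attempt" | Fits as written | Needs an added condition |
| "If both attempts failed to intubate the patient" | Fits: neither approach allowed intubation | Fits |
| "Mechanical ventilation started right after the airway establishment" | Fits | Fits |
| "The Cormack-Lehane grading during Miller versus Macintosh approaches was compared using the McNemar-Bowker test" | Fits: every patient is a pair | Only a selected subset are pairs |

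The first reading satisfies every row as it stands. The second needs a condition that is not in the text. The ventilation sentence says only that ventilation follows the tube, so it does not separate the two readings.

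**Size under each reading, with no true difference**

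The test statistic is the sum over grade pairs i<j of (n_ij − n_ji)² / (n_ij + n_ji), referred to chi-square with one degree of freedom per non-empty pair. The level of 0.05, two-sided, comes from the Statistics section. The rest is assumed:

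- N = 100, 200 or 400
- latent correlation between the two views of 0.6 or 0.8
- grades 1 to 4 at 60/25/12/3% or 75/18/6/1%
- probability of failed intubation by grade of 2/10/50/90%

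That makes 3 × 2 × 2 = 12 scenarios, each with 1,500 simulated trials.

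The expected share of patients failing the first attempt is:

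- first distribution: 0.60×0.02 + 0.25×0.10 + 0.12×0.50 + 0.03×0.90 = 0.124
- second distribution: 0.75×0.02 + 0.18×0.10 + 0.06×0.50 + 0.01×0.90 = 0.072

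| Who has both grades | Better | Worse | Rejection rate |
|---|---|---|---|
| Everyone | 11–21% | 11–21% (equal) | 1.5–3.9% |
| Everyone, then double failures dropped | 11–20% | 11–20% (equal) | 1.6–3.7% |
| First failures only | 40–54% | 9–11% | see below |
| First failures only, double failures dropped | 46–65% | 5–6% | see below |

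Over the last two rows, rejection is 1–6% at N = 100, 7–45% at N = 200 and 29–95% at N = 400.

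**A second set of assumptions**

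Suppose 17% of patients have conventional grade 3 or 4, and only they receive a Miller grade. Assumed change probabilities, as shares of all patients, are 3→2 0.020, 3→1 0.0025, 4→3 0.005 and 3→4 0.005.

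- Better: 0.020 + 0.0025 + 0.005 = 0.0275
- Worse: 0.005
- Ratio: 0.0275 / 0.005 = 5.5

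| Enrolled | Non-empty-pair df | 6 df | Change probabilities halved, non-empty-pair df |
|---|---|---|---|
| 100 | 8% | below 0.1% | 1% |
| 200 | 35% | 0.3% | 8% |
| 300 | 64% | 5% | 21% |

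The direction is stable under this reading. The size is set almost entirely by assumptions the documents do not supply.

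**Would the selection go unseen?**

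In the first distribution, conventional grade 1 accounts for 60% of patients but only 0.60×0.02 / 0.124 = 0.012 / 0.124 ≈ 10% of the selected pairs, and pairs would number about 12% of those enrolled. Both would show in the cross-table from which the test is computed.

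**The case for a change.** The strongest case for acting starts from the drop-out rule, which has meaning only if each approach can succeed or fail at intubation. The section places the gradings within intubation and never says at which view the tube goes in. If even some patients were intubated at the first view, their Miller grade would be missing, and the Statistics section does not say how to treat them. The resulting bias has a known direction and a clarifying sentence would cost little.

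Part of this stands. The word attempt is used loosely, and the timing of tube passage is not written down. Two stronger claims do not stand. That a tube is tried at each view is an inference: the rule describes the case where neither approach works, and does not say that a first success cancels the second view. That the sentences cannot all be followed is true only if one first assumes the tube is passed at the first view, which no sentence says. Equating a failed attempt with grade 3 or 4 is likewise an assumption; the protocol makes no such link.

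**Conclusion.** No change is called for. Followed as written, the protocol yields two grades in every patient, the paired test has what it needs, and the selection bias is zero. Dropping patients in whom both approaches fail does not disturb this, provided failure depends on grade in the same way for both approaches, as assumed in the simulation.

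The bias would arise only if the second view were conditional on failure of the first. It would then favour the Miller approach, with a false-positive rate anywhere from about 1% to 95% over the assumed scenarios, so no single figure can be attached to this trial. What is left is a gap in wording that staff and analysts would fill sensibly: spelling it out would only record what the plainer reading already does. A departure large enough to matter would be visible in the number of complete pairs and in a thin row for good conventional views. The fixed order of the two views is a separate question and does not enter these figures.

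### Patients in whom both intubation attempts fail leave the study after both Cormack-Lehane grades are recorded, so complete endpoint pairs are lost because of a later, related result

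*Combined protocol and SAP*

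**What the plan says.** The Anesthesia protocol section sets out a sequence within each patient.

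1. The blade is placed for the conventional (Macintosh) view: "Cormack-Lehane grade was then record as conventional attempt".
2. The blade is moved under the epiglottis for the second view: "Cormack-Lehane grade was record as Miller's attempt".
3. A rule for failure follows. "If both attempts failed to intubate the patient", then "the process would switch to emergent difficult airway protocol and the patient would drop out the research".

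The Statistics section names one comparison: "The Cormack-Lehane grading during Miller versus Macintosh approaches was compared using the McNemar-Bowker test". It is two-sided at 0.05. That section defines no analysis set, does not say what happens to grades already recorded for patients who drop out, and plans no count of them.

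**The concern.** The rule removes a patient on the basis of something seen after enrolment and, in the order described, after both halves of the endpoint have been recorded. The endpoint is not missing for these patients. It has been observed and is then set aside.

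The trigger is failure to intubate with either approach. Laryngeal view and intubation success are plausibly related, so the patients removed are likely to include some of the poorest views. The comparison is then restricted to patients who could be intubated by at least one approach, which is not the population enrolled under the Patient section.

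Two things are at stake. The reported shares of poor views would probably look too favourable for both approaches. The McNemar-Bowker test would also lose any double failure with unequal grades. The rule is symmetric: a pair that improves from grade 4 to grade 3 is dropped just as one that worsens from 3 to 4. There is therefore no claim that it favours either approach. With no count planned, a reader could not judge the effect.

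**Working it through.** **Inputs.** The documents give the order of events, the test and the 0.05 level. They give no sample size, grade distribution or failure rate, so there is no figure of the plan's own to reproduce. Every count below is assumed for illustration.

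**How many patients might be removed.** The chance of at least one double failure among n patients with failure rate f is 1 − (1 − f)^n. For n = 200:

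| Assumed f | Expected removals | Chance of at least one |
|---|---|---|
| 0.2% | 0.4 | 0.33 |
| 1% | 2 | 0.87 |
| 3% | 6 | 0.998 |

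**Effect on frequencies.** Assume 200 patients, grade 3-4 in 30 with Macintosh and 12 with Miller, 10 of them in both. Let k of those 10 be double failures. The shares become (30 − k)/(200 − k) and (12 − k)/(200 − k), with paired difference 18/(200 − k).

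| k dropped | Macintosh | Miller | Difference (points) |
|---|---|---|---|
| 0 | 30/200 = 15.0% | 12/200 = 6.0% | 9.0 |
| 1 | 29/199 = 14.6% | 11/199 = 5.5% | 9.05 |
| 2 | 28/198 = 14.1% | 10/198 = 5.1% | 9.09 |
| 5 | 25/195 = 12.8% | 7/195 = 3.6% | 9.23 |

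Both shares fall; the difference barely changes.

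**Effect on the test.** The statistic is the sum of (a − b)²/(a + b) over pairs of off-diagonal cells. Equal-grade patients do not enter it. This is a separate hypothetical table. Take an analysed set that is borderline, with counts worse v better under Miller of 8 v 14 (grades 1-2), 3 v 9 (grades 2-3) and 0 v 4 (grades 3-4). Degrees of freedom are the 3 non-empty cell pairs.

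- Base: 36/22 + 36/12 + 16/4 = 8.64, p = 0.035.

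Now restore double failures, all of one type (Macintosh grade to Miller grade):

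| Type restored | 3 restored: statistic | p | 1 restored: statistic | p |
|---|---|---|---|---|
| 4 and 4 | 8.64 | 0.035 | 8.64 | 0.035 |
| 3 to 4 | 36/22 + 36/12 + 1/7 = 4.78 | 0.19 | 6.44 | 0.092 |
| 2 to 3 | 36/22 + 9/15 + 16/4 = 6.24 | 0.10 | 7.56 | 0.056 |
| 4 to 3 | 36/22 + 36/12 + 49/7 = 11.64 | 0.009 | 9.64 | 0.022 |

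With a strong effect (8 v 24, 2 v 18, 0 v 4) the base is 256/32 + 256/20 + 16/4 = 24.8. Restoring 3 patients gives 20.9 (3 to 4), 19.3 (2 to 3) or 27.8 (4 to 3). All have p < 0.001 on 3 degrees of freedom.

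**Sensitivity to the degrees of freedom.** The plan states no convention for empty cell pairs. Counting all 6 pairs of a four-grade table, the base of 8.64 gives p = 0.195 and three restored 4-to-3 pairs give 0.071, so this table is no longer borderline. In the strong case the largest p-value is 0.0036, from three 2-to-3 pairs.

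**The case against.** The strongest reply is that dropping out may mean only leaving the study procedure. The phrase sits in a sentence about a change of airway management, and the Statistics section never says that recorded grades are discarded. That is true. But leaving the research is stated in addition to the switch of protocol, so exclusion is the natural reading. If the sponsor meant something else, the same added sentence settles it.

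Second, a complete pair is inferred from the order of the text; in some failed cases the second view might never have been graded. That stands as a limit, and the remedy covers only patients with both grades recorded.

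Third, the number is probably small. Removal needs failure of both approaches. The patients are ASA I-II, and the exclusions include emergent surgery, "Limited mouth opening", airway obstruction and deep neck infection. A video blade is used by three physicians, each described as having more than 300 successful intubations. This stands: the case of 5 in 200 has no basis in the documents.

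Fourth, the p-values come from invented tables, with all restored patients placed in one cell, and they depend on the degrees of freedom. Another assumed table with p = 0.044 moves to 0.016 when six 3-to-4 pairs are restored, whereas the 3-to-4 case above moves p upward. That also stands. The figures show that the result can move either way, not what happened in this trial. The objection to the rule does not depend on them.

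**Conclusion.** The concern holds. Followed as written, the plan excludes patients with a complete endpoint pair because of a later result that is plausibly related to the endpoint. Poor-view frequencies are probably understated for both approaches. In the assumed example the understatement runs from about half a point (1 dropped) to a little over 2 points (5 dropped), with the paired difference almost unchanged. The test is affected only through double failures with unequal grades, in an unknown direction, and its conclusion is at risk only near the threshold.

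This rests on reading the drop-out rule as exclusion from analysis and on both grades having been recorded before the rule applies. The true size cannot be worked out from the documents and may be small. It is a selection problem that should be corrected because it is avoidable at little cost and, with no count planned, would otherwise be invisible.

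**What to change.** Add one sentence to the Anesthesia protocol section: a patient in whom both attempts fail leaves the study procedure for airway management, as now, but grades already recorded are kept. Add one to the Statistics section: every patient with both grades recorded enters the grade frequencies and the McNemar-Bowker comparison whatever the intubation result, and the number of double failures is reported with their grade pairs. Showing the comparison without them as a sensitivity analysis would also help.

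No new measurement is needed. Recruitment is described as running from October 2019 to January 2022, and the documents do not say whether dropped patients' records were kept, so the grades may have to be retrieved. If they cannot be, the count should still be reported. The downside is that reported poor-view rates may become slightly less favourable.
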